12.3. Missing Data

Missing data will be tracked in the Electronic Data Capture system; queries will be generated and provided to the site. In addition, a St. Jude Medical representative, or designee will routinely perform monitoring visits at each site. During the monitoring visits, missing data queries will be addressed until resolution. Missing data that are not resolved will not be imputed unless specified in the sections below.

12.4. Subject Accountability and Baseline Information

Descriptive summaries will be generated to describe the disposition of all enrolled subjects.

12.5. Demographic and Baseline Information

Descriptive summaries will be generated for all relevant baseline variables. These variables include, but are not limited to, demographic data and conditions at the time of enrollment.

12.6. Safety Analyses

The safety analyses will be performed using the Safety Population. The data will be summarized using univariate statistics (e.g., N, mean, standard deviation, median, minimum and maximum) or frequency (e.g., N, %) as appropriate.

12.6.1. Primary Safety Endpoints

The primary safety analyses will be based on the following objective performance criteria: a) the lower limit of the two-sided 95% confidence interval on the freedom from device / system-related complication rate at 24 months is greater than 80% and b) the lower limit of the two-sided 95% confidence interval on the freedom from pressure sensor failure rate at 24 months is greater than 90%. These primary safety endpoints will be tested hierarchically in order to control for multiplicity. First, the freedom from device / system-related complication rate will be tested. If the result is statistically significant (i.e., $p < 0.050$), then the freedom from pressure sensor failure rate will also be tested for significance (i.e., $p < 0.050$). The study will be judged to have provided positive safety results if both tests of the primary safety analysis endpoints are statistically significant (i.e., $p < 0.050$).

Mathematically stated, the primary safety hypotheses are:

a) $H_0: P_{(\text{Freedom from device / system-related complications at 24 months})} \leq 80\%}$

$H_a: P_{(\text{Freedom from device / system-related complications at 24 months})} > 80\%$

b) $H_0: P_{(\text{Freedom from pressure sensor failure at 24 months})} \leq 90\%$

$H_a: P_{(\text{Freedom from pressure sensor failure at 24 months})} > 90\%$

Plotting and analysis of safety endpoints will also be displayed using Kaplan-Meier methods.

This confidential document is the property of Abbott and shall not be reproduced, distributed, disclosed or used without the express written consent of Abbott

Clinical Investigation Plan

Safety will also be assessed throughout the study by the frequency of Adverse Events (AEs), Adverse Device Effects (ADEs), Serious AEs (SAEs), and Serious Adverse Device Effects (SADEs), and device / system-related complications by relationship to the device via Medical Dictionary for Regulatory Activities (MedDRA) system organ classification. Physical examination, and subject survival data through 24 months will be tabulated across study period assessments.

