12.1. Populations for Analysis

Safety Population: The Safety Population consists of all subjects who received a Sensor implant or underwent the implant procedure but were never implanted, regardless of study completion status. All safety analyses will be performed on the Safety population.

Subjects who are found not to have an appropriately sized pulmonary artery branch and did not receive the Sensor implant will be considered ineligible for the study. However, these subjects will be followed for 30 days for safety and all safety related data for these subjects will be provided.

Effectiveness Population: The effectiveness population consists of all subjects who received a Sensor implant regardless of study completion status. All effectiveness analyses will be performed on the effectiveness population.

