12.2. Sample Size Considerations

Effectiveness Sample Size Determination

For the primary effectiveness endpoint of HF hospitalization rate during 1 year, 300 patients will provide greater than 90% power to meet the efficacy goal (upper confidence limit less than the HF hospitalization rate in the year prior to enrollment), using a one-sample, two-sided Poisson confidence interval with alpha of 0.05.

Safety Sample Size Determinations

For the two-year primary safety endpoint of freedom from device-related complications, using an exact two-sided test for one-sample binomial proportions with alpha of 0.05, a sample size of 619 subjects will provide greater than 90% power to detect a difference as small as 5% from the null proportion rate of 0.80 (i.e., objective performance criterion of 80%). For sensor failures at 2 years, a sample size of 663 subjects provides greater than 90% power to detect a difference as small as 3.5% from the null proportion rate of 0.90 (i.e., objective performance criterion of 90%).

This confidential document is the property of Abbott and shall not be reproduced, distributed, disclosed or used without the express written consent of Abbott

Clinical Investigation Plan

Thus, the sample size for this study is driven by the safety endpoints. The 2 year attrition rate in CHAMPION was 49.1% (228/550). To ensure sufficient patients are enrolled to adequately evaluate safety and efficacy, 1200 subjects will be enrolled.

Note that at least 35% of the 1200 enrolled patients (420) must be women resulting in approximately 206 women completing the trial (assuming a 49% attrition rate). This sample size will provide greater than 90% power to meet the goal for effectiveness. Regarding freedom from device-related complications and freedom from sensor failures, 206 women will provide greater than 90% power to detect a difference as small as 0.06 from the null proportion rate of 0.90.

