13.9.3. Schematic Diagram of the Sub-study and Main PAS Study

See Appendix M for a schematic diagram of the Main PAS Study and the PAS Sub-study.

REPORTING OF INTERIM AND PRIMARY ANALYSES

In addition to the primary safety and effectiveness analyses, updates from the PAS will be submitted to FDA as a PMA supplement every 6 months for the first two years of the study (annually thereafter) and updated in the device labeling. This information will include the following: study enrollment and follow-up status; demographic information; safety and effectiveness results; mortality; serious adverse events; days alive outside of the hospital for heart failure; patient compliance; sensor performance; and medication changes in response to PA pressure. Please refer to Appendix L: Reporting of Interim Analyses.

The primary safety analyses will be reported after all patients complete 24 months post enrollment or discontinue early. The primary effectiveness analyses will be reported after all patients complete 12 months post enrollment or discontinue early.

CLINICAL EVENTS COMMITTEE

An independent clinical events committee (CEC) will be formed to review clinical data. The committee will be comprised of physicians, who will not participate in the enrollment or treatment of subjects in this trial. All endpoints or suspected endpoints will be reviewed by this committee according to the CEC Committee charter. Any event listed in the CEC Committee charter reported in an SAE report or the CRF will trigger the accumulation of a portfolio of pertinent documents from the hospital admission. These documents will be collected and copies distributed to members of the CEC Committee. The

This confidential document is the property of Abbott and shall not be reproduced, distributed, disclosed or used without the express written consent of Abbott

Clinical Investigation Plan

interpretation of the event as classified and adjudicated by the clinical events committee will be used in the final effectiveness and safety analyses.

The composition and function of the CEC Committee is described in Appendix K.

DATA COLLECTION, STUDY MONITORING, AND DATA DISCLOSURE

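### The 24-month safety tests do not say how subjects who leave event-free before 24 months are counted; at the assumed attrition that rule can decide the result

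*Combined protocol and SAP*

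**What the plan says.** Section 12.6.1 tests two endpoints in sequence. The lower limit of the two-sided 95% "confidence interval on the freedom from device / system-related complication rate at 24 months is greater than 80"%, and then the corresponding limit for freedom from sensor failure must exceed 90%. Section 13.9.1 sets the same structure for the sub-study. Neither section gives a rule for a subject with less than 24 months of follow-up.

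Other parts of the plan point in different directions:

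- **Section 12.6:** "The safety analyses will be performed using the Safety Population". By Section 12.1 that population "consists of all subjects who received a Sensor implant or underwent the implant procedure but were never implanted, regardless of study completion status".
- **Section 12.2** sizes the complications endpoint "using an exact two-sided test for one-sample binomial proportions with alpha of 0.05", giving 619 subjects. For sensor failure, "a sample size of 663 subjects provides greater than 90% power". It then says "The 2 year attrition rate in CHAMPION was 49.1% (228/550") and raises enrollment to 1200, which suggests an analysis of completers without saying so.
- **Section 12.3** says that unresolved missing data are not imputed unless a later section specifies it. The safety sections specify nothing.
- **Section 14:** "The primary safety analyses will be reported after all patients complete 24 months post enrollment or discontinue early". How those who discontinue count is not stated.
- **Section 12.6.1** on survival methods: "Plotting and analysis of safety endpoints will also be displayed using Kaplan-Meier methods". The word *also* makes this an addition to the tested limit, not clearly its source.

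**The concern.** Both primary safety decisions, and their sub-study counterparts, depend on a quantity that the plan leaves undefined for the 41% to 49% of subjects it expects to lose. Three binomial readings are open:

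- **A.** All subjects in the denominator, with early leavers counted as event-free. This can overstate 24-month freedom, because part of the follow-up is unobserved.
- **B.** Events kept wherever they occur, with event-free early leavers dropped. This understates freedom, because it removes only event-free people.
- **C.** Subjects followed to 24 months only. This is roughly unbiased if dropout is independent of the event. For complications, however, it loses the fatal ones, which Section 9.1.1 counts as complications.

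If true freedom is near the OPC, A can pass a device that does not meet it. If true freedom is moderately above the OPC, B can fail a device that does. The study is open-label, so without a written rule the choice could be made after events are known.

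A smaller gap is that never-implanted subjects are in the Safety Population but cannot have a sensor failure. Section 12 defines enrollment as successful implant, so they also have no enrollment date from which to count 24 months.

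**Working it through.** **Inputs from the plan:** OPCs 80% and 90%; alternatives 85% (80 + 5) and 93.5% (90 + 3.5); two-sided 0.05; n=1200; attrition 49.1%, or 228/550 = 41.5% (49.1% of 550 would be 270).

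**Assumptions not in the documents:** independent exponential dropout; a share of events at implant and the rest at constant hazard; all attrition treated as censoring unless stated. Paired figures are complications / sensor failure.

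**Plan's own figures.** The exact binomial test reproduces them. With 619 subjects, at least 515 must be event-free, and power is 90.4%. With 663, at least 612, and power is 90.5%.

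**Formulas** (time unit 24 months). F = 1 − true freedom; q = F × share at implant; h = −ln(true freedom/(1−q)); d = −ln(1−attrition), which is 0.6753 at 49.1% and 0.5354 at 41.5%.

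- Observed failures: f = q + (1−q) × h/(h+d) × (1−e^−(h+d))
- Event-free completers: s = (1−q) × e^−(h+d)

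**Reading A at the OPC.** The exact (Clopper-Pearson) limit passes with at least 988 / 1101 event-free of 1200. Example for complications, half at implant, 49.1%: q = 0.10; h = −ln(0.80/0.90) = 0.1178; f = 0.10 + 0.90 × (0.1178/0.7931) × (1−e^−0.7931) = 0.1732. Apparent freedom is 82.7% when the truth is 80%, and P(X ≥ 988) = 64%.

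| Share of events at implant | False-pass, 49.1% attrition | False-pass, 41.5% attrition |
|---|---|---|
| All | 2.2% / 2.2% | 2.2% / 2.2% |
| 80% | 14% / 8% | 11% / 7% |
| Half | 64% / 34% | 48% / 24% |
| None (constant hazard) | 99.8% / 90% | 97% / 75% |

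If half the attrition hazard is unrelated death and the estimand is cumulative incidence, the constant-hazard row becomes 66% / 36% (49.1%) or 49% / 25% (41.5%). If all attrition is unrelated death, it is 2.2% / 2.2%.

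**Reading B at 85% / 93.5%, constant hazard.** s/(s+f) = 0.7972 / 0.9094 at 49.1% and 0.8097 / 0.9156 at 41.5%. Pass rates, averaged over the random evaluable number, are 1.4% / 10% and 9% / 27%.

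**Reading C.** 1200 × (1−0.491) = 611, below 619 and 663; power 88.9% / 86.6%. At 41.5% attrition, 703 remain; power 92.9% / 90.8%. False-pass is about 2% in each case, ignoring fatal complications.

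**One expected data set, three limits** (49.1%, true freedom 85% / 93.5%, constant hazard). Complications: 132 events, 519 event-free completers, 549 event-free leavers. Sensor failure: 57, 571 and 572.

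| Method | Complications, lower limit (OPC 80%) | Sensor failure, lower limit (OPC 90%) |
|---|---|---|
| A, denominator 1200 | 87.1%, pass | 93.9%, pass |
| Kaplan-Meier, log-log | 82.4%, pass | 91.6%, pass |
| B, denominators 651 / 628 | 76.4%, fail | 88.4%, fail |

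**Where it stops mattering** (49.1%). At true 88% / 95%, constant hazard, A passes 100% / 100% and B 63% / 73%. At 92% / 97%, both pass at least 95% of the time in every timing case.

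**Kaplan-Meier log-log limit, simulated** (n=1200, 3000 runs per case, both attrition rates, all four timing cases): false-pass 1.9% to 2.6%; power at the plan's alternatives 96–99% / 95–99%.

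**Binomial interval formula.** Exact, Wilson and Wald limits on a fixed denominator differ by 0 to 2 events in the pass threshold.

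**The case against.** A reader might infer that the plan, read literally, prescribes a crude proportion over all 1200 subjects. The documents do not support that. Section 12.1 points that way, but Section 12.3 bars imputation, and calling an unobserved 24-month status event-free is arguably imputation. Section 12.2 sizes as if for completers and speaks of about 206 women completing. Under the completer reading the harm is limited: false-pass stays near 2%, and power falls slightly short at 49.1% attrition. This objection stands, so reading A is one possibility and not the plan's stated method.

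A reader might also take the 99.8% as the expected size of the problem. It needs true freedom exactly at the OPC, no events at implant and all attrition treated as censoring. Section 11.6 lists several procedural events, such as catheter-site bleeding and vessel perforation, so a complete absence of implant events is implausible for complications. Earlier timing does not rescue reading B, because it increases the number of observed failures.

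The missing name of an interval formula might look like a defect of its own. On a fixed denominator it is immaterial, and Section 12.2 already names an exact test for sizing.

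Finally, the change is not free. Section 17.2 requires IRB approval and FDA submission for changes that affect validity. Version C is dated 19 February 2018, after the enrollment completion anticipated for December 2017, and interim safety results go to FDA. That is a reason to fix and date the rule before the final analysis. It does not justify leaving the rule open.

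**Conclusion.** The gap is real and should be fixed. Sections 12.6.1 and 13.9.1 give no rule for event-free early leavers, other sections point to conflicting rules, and each binomial reading has a defect. A can be anti-conservative by an amount that depends on event timing and on the treatment of death. B usually fails a device that performs at the plan's own alternatives. C drops fatal complications and, at the printed attrition, falls below the sized numbers.

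The sizes rest on independent dropout and on assumed event timing. The documents give no expected event rates beyond the sizing alternatives of 85% and 93.5%, which lie inside the affected range. If true freedom is about 92% / 97% or better, A and B agree. The documents do not show that an unsafe device would pass, or that the sponsor intends reading A. They show only that the decision rule is incomplete.

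**What to change.** In Sections 12.6.1 and 13.9.1:

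- Make the Kaplan-Meier estimate of 24-month freedom, with its two-sided 95% log-log (Greenwood) lower limit, the decision statistic for both OPCs. Take the hierarchical p-values from the same statistic and keep the crude proportion as descriptive.
- Censor event-free subjects at withdrawal, last contact or unrelated death. As the sensitivity analysis, use cumulative incidence with unrelated death as a competing event.
- Analyse sensor failure in implanted subjects from the implant date. Keep never-implanted subjects in the complications analysis from the procedure date, censored at last follow-up.
- In Section 12.2, reconcile 49.1% with 228/550 and restate the power accordingly.

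Cost: no new data are needed, and Kaplan-Meier output is already planned. The interval is slightly wider than for a crude proportion (simulated half-width at n=1200, constant hazard: 2.6 to 2.7 points against 2.3 for complications, and 2.0 against 1.7 for sensor failure). The method relies on non-informative censoring, which the sensitivity analysis probes only for death. It needs a protocol amendment, fixed and dated before the final safety data are analysed, because the study is open-label with interim reports.

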12.7. Effectiveness Analyses

Effectiveness analyses will be conducted in the effectiveness population. The data will be summarized using univariate statistics (e.g., N, mean, standard deviation, median, minimum and maximum) or frequency (e.g., N, %) as appropriate.

12.7.1. Primary Effectiveness Endpoint

The primary time point for analyses is 12 months post-enrollment. The primary effectiveness endpoint will compare the annualized HF hospitalization rate parameter, γ , at 1 year versus the HF hospitalization rate in the year prior to enrollment using a two-sample, two-sided Poisson confidence interval. If the two-sided, upper 95% confidence interval for the PAS rate parameter is less than that in the year prior to enrollment, then the primary effectiveness endpoint will be met.

Mathematically stated, the primary effectiveness hypothesis is:

$$H_0: \gamma_{(12 \text{ month HF Hospitalization Rate})} \geq \gamma_{(\text{HF hospitalization rate in year prior to enrollment})}$$

$$H_a: \gamma_{(12 \text{ month HF Hospitalization Rate})} < \gamma_{(\text{HF hospitalization rate in year prior to enrollment})}$$

where $\gamma_{(12 \text{ month HF Hospitalization Rate})}$ = the HF hospitalization rate parameter at 1 year in the PAS and $\gamma_{(\text{HF hospitalization rate in year prior to enrollment})}$ = the HF hospitalization rate in the year prior to enrollment.

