Device:	The CardioMEMS HF System consists of a wireless, battery-less pressure sensor implanted into the pulmonary artery and an external electronics that powers and communicates with the sensor and transmits pulmonary artery pressure waveforms and measurements to a secure website for Investigator review and patient management.
Purpose:	The purpose of this Post Approval Study (PAS) is to evaluate the use of the CardioMEMS HF System in patients with Class III Heart Failure (HF) in a commercial setting.
Objective:	The objective of this PAS is to confirm safety and effectiveness in a commercial setting.
Study Population:	
Adults with New York Heart Association (NYHA) Class III Heart Failure who have experienced a heart failure hospitalization within the past 12 months. At least 35% of the enrolled patients will be women.
 
The patients will serve as their own historical controls for effectiveness (1 year prior implantation).
 
All subjects who sign the informed consent form and satisfy the inclusion/exclusion criteria.
 
Ejection fraction data must be taken within the last 3 months to enroll in the study.

Study Design:	
This is a prospective, multi-center, open-label trial conducted in the United States (US).
 
All subjects who sign the informed consent form and satisfy the inclusion/exclusion criteria will be enrolled into the CardioMEMS HF System PAS and will be scheduled for follow-up visits at 1 month and every 6 months for 2 years.
 
Following sensor implant and hospital discharge, subjects will take PA pressure measurements on a daily basis, or as directed by the investigator. These measurements will be automatically transmitted to the secure Patient database (CardioMEMS HF website).

Timeline:	Study visits will be scheduled at Month 1, Month 6, and every 6 months thereafter for 2 years or until study termination.

This confidential document is the property of Abbott and shall not be reproduced, distributed, disclosed or used without the express written consent of Abbott

Clinical Investigation Plan

Number of Subjects	Twelve hundred subjects will be enrolled with at least 35% of the enrolled patients being women (420 women out of 1200). Enrollment will be limited to 15% of the total study population at any one site.
Number of Sites:	This is a prospective, multi-center, open-label clinical trial to be conducted at up to 150 sites.

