11.6.2. Anticipated ADEs/SADEs

The following is a list of possible anticipated ADEs/SADEs:

- Hemoptysis
- Sensor not deploying
- Transient ischemic attack
- Atypical chest pain
- Sepsis leading to death
- Atrial arrhythmia leading to death
- Arterial embolism (upper extremity)
- PA (in-situ) thrombus
- Catheter site bleeding
- Catheter site ecchymosis
- Catheter site hematoma
- Vessel puncture site pain
- Cardiac monitoring abnormal
- Heart rate irregular
- Serum creatinine increased
- Dyspnea
- Congestive HF
- Ventricular tachycardia
- Dizziness
- Vessel perforation
- Sensor failure/malfunction
- Sensor migration

This confidential document is the property of Abbott and shall not be reproduced, distributed, disclosed or used without the express written consent of Abbott

Clinical Investigation Plan

- System not transmitting

Refer to the CardioMEMS™ PA Sensor and Delivery Catheter, Model CM2000 User Manual for more information. If it is not certain that an event meets the above definitions, contact the Project Manager.

For unexpected failure modes or unexpected adverse events, the site should follow their standard reporting practices for medical device reporting (MDR). As defined in 21 CFR 803, a MDR reportable event (or reportable event) means: An event that device user facilities become aware of that reasonably suggests that a device has or may have caused or contributed to a death or serious injury. A device user facility must report to sponsor and the FDA (no later than 10 days after awareness date) deaths and serious injuries that a device has or may have caused or contributed to, establish and maintain adverse event files, and submit summary annual reports to FDA.

STATISTICAL ANALYSIS

The data will be summarized using univariate statistics (e.g., N, mean, standard deviation, median, minimum and maximum) or frequency (e.g., N, %) as appropriate.

The primary time point for safety analyses is 24 months post enrollment. Enrollment is defined as having a successful Sensor implant. The primary time point for effectiveness analyses is 12 months post enrollment.

Unless otherwise specified, all statistical tests will be 2-sided with a significance level of 0.05.

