APPENDIX L: Reporting of Interim Analyses

Updates from the PAS will be submitted to FDA as a PMA supplement every 6 months for the first two years of the study (annually thereafter). This information will include the following information:

Study enrollment and follow-up status

This confidential document is the property of Abbott and shall not be reproduced, distributed, disclosed or used without the express written consent of Abbott

Clinical Investigation Plan

Demographic information

	Premarket Study	PAS Aggregate	PAS Male	PAS Female
Average Age (years)	XX.X ± XX.X	XX.X ± XX.X	XX.X ± XX.X	XX.X ± XX.X
Male	XX.X%	XX.X%	XX.X%	XX.X%
Caucasian	XX.X%	XX.X%	XX.X%	XX.X%
Average BMI	XX.X ± XX.X	XX.X ± XX.X	XX.X ± XX.X	XX.X ± XX.X
Average LVEF	XX.X ± XX.X%	XX.X ± XX.X%	XX.X ± XX.X%	XX.X ± XX.X%
LVEF < 40%	XX.X%	XX.X%	XX.X%	XX.X%
Ischemic Cardiomyopathy	XX.X%	XX.X%	XX.X%	XX.X%
Average PA Systolic (mmHg)	XX.X ± XX.X	XX.X ± XX.X	XX.X ± XX.X	XX.X ± XX.X
Average PA Diastolic (mmHg)	XX.X ± XX.X	XX.X ± XX.X	XX.X ± XX.X	XX.X ± XX.X
Average PA Mean (mmHg)	XX.X ± XX.X	XX.X ± XX.X	XX.X ± XX.X	XX.X ± XX.X
Average PA Wedge (mmHg)	XX.X ± XX.X	XX.X ± XX.X	XX.X ± XX.X	XX.X ± XX.X
Average Cardiac Output (L/min)	XX.X ± XX.X	XX.X ± XX.X	XX.X ± XX.X	XX.X ± XX.X
Average Cardiac Index (L/min/m ²)	XX.X ± XX.X	XX.X ± XX.X	XX.X ± XX.X	XX.X ± XX.X

Safety

	6 Months N=XXXX		12 Months N=XXXX		18 Months N=XXXX		24 Months N=XXXX	
	N	Percent	N	Percent	N	Percent	N	Percent
DSRCs	XXX	XX.X%	XXX	XX.X%	XXX	XX.X%	XXX	XX.X%
Pressure Sensor Failures	XXX	XX.X%	XXX	XX.X%	XXX	XX.X%	XXX	XX.X%

Heart Failure Hospitalizations

	6 Months N=XXXX	12 Months N=XXXX	18 Months N=XXXX	24 Months N=XXXX
HF Hospitalizations	XXX	XXX	XXX	XXX
HF Hospitalization Rate:				
Events/patient years	X.XX	X.XX	X.XX	X.XX
Events/patient days	X.XX	X.XX	X.XX	X.XX
HF Hospitalization Proportion	XX.X%	XX.X%	XX.X%	XX.X%

Mortality

	6 Months N=XXXX		12 Months N=XXXX		18 Months N=XXXX		24 Months N=XXXX	
	Deaths	Percent	Deaths	Percent	Deaths	Percent	Deaths	Percent
All Cause Deaths	XXX	XX.X%	XXX	XX.X%	XXX	XX.X%	XXX	XX.X%
Cardiac Deaths	XXX	XX.X%	XXX	XX.X%	XXX	XX.X%	XXX	XX.X%
Non-Cardiac Deaths	XXX	XX.X%	XXX	XX.X%	XXX	XX.X%	XXX	XX.X%

This confidential document is the property of Abbott and shall not be reproduced, distributed, disclosed or used without the express written consent of Abbott

Clinical Investigation Plan

Serious Adverse Events

	6 Months N=XXXX		12 Months N=XXXX		18 Months N=XXXX		24 Months N=XXXX	

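### The primary before-after test weights patients by time followed after implant but equally before it, which can lower the rate ratio modestly with no device effect

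*Combined protocol and SAP*

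**What the plan says.** The Protocol Synopsis sets up a before-after design: "The patients will serve as their own historical controls for effectiveness (1 year prior implantation)". Section 12.7.1 takes the "annualized HF hospitalization rate parameter" and compares it "at 1 year versus the HF hospitalization rate in the year prior to enrollment using a two-sample, two-sided Poisson confidence interval". The endpoint is met "If the two-sided, upper 95% confidence interval for the PAS rate parameter is less than that in the year prior to enrollment". The opening of Section 12 adds: "Unless otherwise specified, all statistical tests will be 2-sided with a significance level of 0.05".

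Three further statements fix the weights.

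- **Start of follow-up** (opening of Section 12): "Enrollment is defined as having a successful Sensor implant". Every analysed patient therefore survived the whole prior year.
- **Population** (Section 12.1): "The effectiveness population consists of all subjects who received a Sensor implant regardless of study completion status". Section 14 runs the primary effectiveness analysis once all patients have reached 12 months or discontinued early, so truncated follow-up is kept.
- **Denominator**: Section 12.7.1 gives none. The only one shown is "Events/patient years", in the interim reporting tables of Appendix L.

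Section 12.3 imputes nothing unless a later section says so, and 12.7.1 does not. Death enters a hypothesis only in the supplemental HF-hospitalization-or-death analysis of Section 12.7.2.

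**The concern.** The two rates average over the same patients with different weights. Before implant each patient has weight 1. After implant each has a weight equal to the fraction of the year followed. If patients with many HF admissions also die sooner, they count fully on the left of the comparison and only partly on the right, and the pooled ratio drops with no change in any patient's own rate.

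This shifts the point estimate, so neither more patients nor a larger variance removes it. The planned interval also treats two counts from the same patients as independent samples. At stake is the size of the reported reduction, which goes to FDA and into the labeling (Section 14).

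**Working it through.** **1. The plan's own figure.** Section 12.2 says 300 patients give more than 90% power with a one-sample Poisson interval. No prior-year or target rate is stated, so this cannot be reproduced. As a check on method, the sub-study figures in Section 13.4 (0.52 against 0.75) do reproduce with the exact one-sample interval: 85.7% at n = 114 (stated 85%) and 90.5% at n = 130 (stated 90%).

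**2. Inputs.** From the documents: N = 1200, nominal 2.5% in the favourable direction, prior-year exposure of 1.0 each, and at least one HF hospitalization in the prior year (Section 7.1, criterion 4). Not in the documents, and therefore assumed: 1-year mortality m of 10-20%, gamma between-patient variance θ of 0.3-1.0 (relative to mean 1), and a death hazard proportional to the patient's own rate.

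**3. Ratio with no device effect and no entry selection.** Each patient has the same rate in both years. With h = [(1−m)^(−θ) − 1]/θ,

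ratio = ∫₀¹(1+θht)^(−1/θ−1)dt ÷ ∫₀¹(1+θht)^(−1/θ)dt.

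Example, θ = 1 and m = 0.15: h = 1/0.85 − 1 = 0.1765. The numerator is 1/(1+h) = 0.850, the denominator is ln(1.1765)/0.1765 = 0.921, and the ratio is 0.923.

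The table gives this ratio, with the simulated chance that the two-sample Poisson rule declares success in parentheses (1200 patients; mean rate 1.2 per year for θ = 0.3 and 1.25 for the other rows).

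| θ | m = 10% | m = 15% | m = 20% |
|---|---|---|---|
| 0.3 | 0.985 (7%) | 0.976 (9%) | 0.968 (13%) |
| 0.5 | 0.974 (10%) | 0.961 (18%) | 0.947 (28%) |
| 1.0 | 0.949 (29%) | 0.923 (55%) | 0.896 (79%) |

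If death is unrelated to the hospitalization rate, the ratio is 1.00 and the error is close to nominal (2-4%). If the denominator were patients instead of patient-years, the ratio would be lower still (0.850 at θ = 1, m = 15%).

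**4. Same weights in both years.** Let a_i be the prior-year count, b_i the follow-up count and t_i the fraction of the year followed. Comparing Σb_i with Σa_i t_i, with variance from the patient-level differences, returns the ratio to 1.00 and the error to 2.0-2.8% for θ = 0.5 and 1.0 in this no-selection model.

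**5. Add the trial's entry rule.** Keep only patients with at least one prior-year event, still with no device effect.

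| Underlying mean, θ | Ratio, no deaths | Ratio, 15% mortality |
|---|---|---|
| 0.75, 0.5 | 0.615 | 0.596 |
| 0.75, 1.0 | 0.673 | 0.645 |
| 0.5, 2.0 | 0.649 | 0.609 |
| 0.75, 2.0 | 0.749 | 0.699 |

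The planned test rejects in 100% of null runs in every row, with or without deaths. Deaths move the ratio by a further 0.02-0.05 here, and by 0.01-0.05 over all settings examined. The matched-weight statistic of step 4 also rejects in 100% of runs. At mean 1.2 and 15% mortality it moves the ratio only from 0.733 to 0.745 (θ = 0.5) and from 0.760 to 0.783 (θ = 1.0).

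**6. Add HF admissions just before death** (no entry selection, m = 15%). Suppose some deaths carry one extra terminal HF admission.

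- θ = 0.5: at 25% of deaths the ratio is 0.996 and the error 3.5%; at 50% the ratio is 1.03 and the error is below 1%.
- θ = 1.0: at 25% the error is 21%; at 50% the ratio is 0.989 and the error 4.5%; at 75% the ratio is about 1.03.

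Under 25% and 50% terminal admissions, the matched-weight ratio is 1.04 and 1.07, and conditional Poisson gives 1.05 and 1.10. The two corrections are related but not identical, and both then lean against the device.

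**The case against.** The strongest objection is that this bias decides nothing here. Section 7.1 selects patients on a prior-year hospitalization, and step 5 shows that this alone drives the test to reject under the null, before and after the correction. That stands, and it limits the point to the size of the estimate.

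A reader might infer from the table in step 3 that the trial's false-positive rate is somewhere between 7% and 79%, and that matching the weights brings it back to about 2.5%. The documents do not support that: those figures come from a model without the entry rule and serve only to isolate the mechanism.

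The direction is also assumed. Step 6 shows that a modest number of terminal admissions cancels or reverses the bias, and the documents contain nothing that settles how common they are. This stands too, although an unquantified cancellation is no ground for leaving the weights unequal.

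Two further objections stand in part. Events per patient-year while alive is a conventional quantity, and 12.7.1 is written in terms of two population rates, so reweighting changes the estimand somewhat; but the patients are declared to be their own controls, which favours a within-patient contrast. And the patient-year denominator is an inference from Appendix L, which is itself a reason to define it.

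Finally, death is visible elsewhere: the supplemental HF-hospitalization-or-death analysis, Kaplan-Meier mortality and days alive outside hospital. The supplemental analysis is a useful partial check (under 1% null rejection at θ = 1 without entry selection), but it counts deaths on one side only and does not govern the primary decision.

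**Conclusion.** The concern holds in a limited form. The unequal weighting follows from the design, given a patient-year denominator. It lowers the ratio with no device effect if death risk rises with a patient's own HF hospitalization rate and terminal HF admissions do not offset it. Without entry selection the fall is roughly 2-10% for assumed mortality of 10-20% and variance of 0.3-1.0. With the actual entry rule it adds about 0.01-0.05 to a ratio already pulled down to about 0.6-0.8 by selection.

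It would go too far to say that the estimate is certainly biased toward benefit by this route, or that correcting it makes the primary test valid; the documents support neither. Severity is minor to moderate.

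**What to change.** In Section 12.7.1:

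1. Define the follow-up denominator explicitly, for example patient-years from implant to the earliest of 12 months, death or study exit.
2. Replace the independent two-sample Poisson interval with a within-patient comparison: a conditional Poisson model with log follow-up time as offset and robust variance, or Σ(b_i − a_i t_i) with patient-level variance. Name one as primary, because they do not give identical answers.
3. Keep the crude events per patient-year rates as description, and read the result alongside the HF-hospitalization-or-death analysis.
4. State that selection on a prior-year hospitalization is a separate and larger limitation that this change does not address.

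The cost is SAP wording and a few lines of code, using counts and follow-up times already collected; no new data or patients are needed. The estimated reduction will probably be slightly less favourable, patients with short follow-up contribute less information, and the method is sensitive to HF admissions clustered just before death.
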